10.0 EFFICACY ANALYSES

The efficacy of eluxadoline will be based on eDiary measures related to improvements in IBS-D signs and symptoms. Participants will be required to access the eDiary each evening, preferably at the same time each day, to record daily IBS symptoms.

The efficacy analyses will be based on the mITT Population. Baseline for efficacy based on eDiary measures will be determined for the respective scores average over 14 days prior to the first dose of study treatment. Baseline for efficacy based on study visit measures (IBS-QoL and 7 α C4) will be the last assessment before the first dose of study treatment. Continuous variables will be summarized by number of participants and mean, SD, median, minimum, and maximum values. Categorical variables will be summarized by number and percentage of participants. All efficacy endpoints will be summarized by participant group (BAM or Non-BAM).

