Infrequent, medically important risks reported with eluxadoline in clinical studies were (1) mild transient pancreatitis or rapidly reversible elevation of transaminases associated with abdominal pain, both consistent with sphincter of Oddi (SO) spasm or biliary sludge, and (2) pancreatitis associated with heavy alcohol consumption. Some of these events led to brief hospitalizations, but all had favorable outcomes with no sequelae. There were 13 cases that were adjudicated as SO spasm with an overall occurrence rate of 0.58%. Cholecystectomy status was known in 12 of the 13 patients, and all 12 patients where status was known had no gall bladder. In the postmarketing setting, severe cases of acute pancreatitis, sometimes fatal, were observed following the use of eluxadoline in patients without a gallbladder. Because of this, use of eluxadoline in patients without a gallbladder is contraindicated.

More detailed information about the known and expected benefits and risks and reasonably expected AEs of eluxadoline may be found in the Investigator's Brochure (IB) and/or package insert.

4. Objectives and Endpoints

Objectives	Endpoints
Primary	

 To evaluate the efficacy of eluxadoline 100 mg BID in IBS-D participants with evidence of BAM compared to IBS-D participants without evidence of BAM To evaluate the safety and tolerability of eluxadoline 100 mg BID in IBS-D participants with evidence of BAM and in IBS-D participants without evidence of BAM 	
 Change from baseline in average BSFS score over 4 weeks of treatment period Evaluation of adverse events, clinical laboratory tests, vital signs, physical examinations
Secondary	

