The study will enroll an IBS-D population similar to that enrolled in the Phase 3 studies of eluxadoline. Participants will meet the Rome IV criteria for IBS-D, which differs from the Rome III criteria used in the Phase 3 studies primarily in eliminating abdominal discomfort as a distinct entity from abdominal pain in the definition of IBS-D ([Lacy 2016](#)). Evidence of BAM will be determined by a screening serum $7\alpha\text{C}4$ value $\geq 52.5 \text{ ng/mL}$, which has previously been utilized as a diagnostic cutoff for BAM based on this value being greater than the 95th percentile of serum $7\alpha\text{C}4$ values from 184 healthy controls ([Vijayvargiya 2017](#)).

In order to have comparable treatment groups, the cohorts will be matched to the highest extent possible by age, gender and severity of historic symptoms based on the investigator's discretion.

Improvements in bowel symptoms will be measured during the study. Stool consistency is a highly sensitive efficacy marker, making it ideally suitable to detect potential differences in responsiveness to treatment among participants with and without evidence of BAM. The primary outcome measure for this study will therefore be changes from baseline in stool consistency scores over the 4-week treatment period. Changes from baseline are considered more appropriate than monthly responder definitions given the small pilot nature of this study.

Table 5-2 Current and future and bile acid diarrhea (BAD) diagnostic tests

Diagnostic Test	Fasting serum C4	Total fecal BA	Primary BA >4% + total fecal BA	Fecal primary BA >10%
What does it measure	Hepatic bile acid synthesis	Total fecal bile acid excreted from the colon	Amount of bile acids with secretory potential with total fecal BA excretion	Amount of bile acids that are directly synthesized from the liver with secretory potential
Diagnostic Cutoffs	$\geq 52.5 \text{ ng/mL}$	$\geq 2,337 \mu\text{mol}/48\text{h}$	Primary BA $\geq 4\%$ + total fecal BA $\geq 1,000 \mu\text{mol}/48\text{h}$	$\geq 10\%$ Primary BA
Sensitivity relative to fecal weight $>400\text{g}/48\text{h}$	15%	59%	46%	49%
Specificity relative to fecal weight $>400\text{g}/48\text{h}$	86%	92%	97%	91%

Source: [Vijayvargiya 2018](#)

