10.3.1. Key Statistical Methodology

The methodologies defined in [Table 10-2](#) apply as specified to individual endpoints. All efficacy endpoints will be summarized by participant cohort (BAM or Non-BAM) descriptively.

Table 10–2 Statistical Methodology

Methodology	Description
Categorical counts	
 Number of participants in individual categories 
 Participants with ≥ 1 qualifying event counted once per individual category
Categorical descriptives	
 Number and percentage of participants in individual categories 
 Participants with ≥ 1 qualifying event counted once per individual category [Optional] N1 if percentage denominator \neq number of participants in the population (standard percentage denominator) 
 N1 = participants with nonmissing baseline value
PCS descriptives	
 Number and percentage of participants meeting PCS criteria 
 Participants with ≥ 1 qualifying event counted once per PCS category Percentage denominator = number of participants with nonmissing baseline and ≥ 1 nonmissing postbaseline assessment 
 Unevaluable assessments considered missing
Event descriptives	
 Number and percentage of events in individual categories 
 Events counted individually for each instance Percentage denominator = total number of events
Shift analysis	
 Number and percentage of participants in individual baseline and postbaseline categories Percentage denominator = number of participants in individual baseline categories N1 = participants with nonmissing values at both baseline and the specified postbaseline analysis visit
Continuous descriptives	
 N1, mean, SD, median, minimum, maximum N1 = participants with nonmissing value
CFB descriptives	
 Continuous descriptives for baseline, postbaseline, and CFB values N1 = participants with nonmissing values at both baseline and the specified postbaseline analysis visit

CFB = change from baseline; PCS = potentially clinically significant

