10.3.2. Efficacy Analyses

The following primary and secondary efficacy endpoints will be summarized by cohort (BAM or Non-BAM) for the mITT population. All other efficacy endpoints and analyses will be defined in the SAP.

Descriptions in [Table 10–3](#) and [Table 10–4](#) may be linked to the assessment(s) and/or objective(s).

Table 10–3 Primary Efficacy Endpoint

Endpoint	Description	Timing	Methodology
	Change from baseline in average BSFS	Treatment Period	Descriptive

Endpoint	Description	Timing	Methodology
	score over 4 weeks of treatment period		summary

Note: Analysis visits will be in the SAP.

BSFS = Bristol Stool Form Scale

Table 10-4 Secondary Efficacy Endpoints

Endpoint	Description	Timing	Methodology
	Change from baseline in the 4-week average of daily bowel movement frequency during the treatment period	Treatment Period	Descriptive summary
	Change from baseline in the 4-week average of daily worst abdominal pain scores during the treatment period	Treatment Period	Descriptive summary
	Change from baseline in the 4-week average of daily worst abdominal pain scores during the treatment period	Treatment Period	Descriptive summary
	Change from baseline in the 4-week average of urgency-free days in a week during the treatment period	Treatment Period	Descriptive summary
	Change from baseline in the 4-week average of daily bloating scores during the treatment period	Treatment Period	Descriptive summary
	Change from baseline in IBS-QOL score at the end of the treatment period	Treatment Period	Descriptive summary
	Change from baseline in serum 7αC4 levels at the end of the treatment period	Treatment Period	Descriptive summary
	Proportion of participants with any fecal incontinence during the treatment period	Treatment Period	Descriptive summary

Note: Analysis visits will be in the SAP.

7αC4 = 7α-hydroxy-4-cholesten-3-one; IBS-QOL = irritable bowel syndrome-quality of life

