4.0 INTRODUCTION

[figure not shown]
This statistical analysis plan (SAP) provides a more technical and detailed elaboration of the statistical analyses of the efficacy and safety data as outlined and/or specified in the final protocol of Study 3030-401-002 dated 19 Oct 2017 and the most recent amendment dated 17 Apr 2019. Specifications of tables, figures, and data listings are contained in a separate document. The SAP for pharmacokinetic will be prepared separately.

Study 3030-401-002 is a Phase 4, non-randomized, open-label, parallel-group, cohort controlled trial to evaluate the efficacy, safety, tolerability and pharmacokinetics of eluxadoline in participants meeting the Rome IV criteria for IBS-D with and without evidence of BAM. This study will be comprised of a 0 to 2-week screening period, a 2 to 3-week pretreatment period, a 4-week open-label treatment period during which time participants will receive eluxadoline 100 mg BID, and a 2-week post-treatment safety follow-up.

[figure not shown]
There will be 24 participants enrolled in the study, 12 with evidence of BAM and 12 without evidence of BAM. Cohort 1 consists of IBS-D participants with evidence of BAM treated with eluxadoline 100 mg oral tablets BID with food. Cohort 2 consists of IBS-D participants without evidence of BAM treated with eluxadoline 100 mg oral tablets BID with food. The 100 mg BID dose selected for this trial is consistent with US and global labeling for eluxadoline in IBS-D. This non-randomized design is considered most appropriate since the cohort assignment will be based on the determination of BAM status. As far as possible, the 2 cohorts will be matched by age, gender and severity of historic symptoms based on the investigator's discretion.

[figure not shown]
The total duration of the study is up to 11 weeks, which includes: screening period (1-2 weeks), pretreatment period (2-3 weeks), 4-week open-label treatment period, and 2-week post-treatment follow-up period. A total of 6 study visits are planned for each participant: Screening, Week -3 to -4 (Visit 1); Pretreatment, Week -3 to -2 (Visit 2); Day 1 (Visit 3; first administration of study drug); Week 2 (Visit 4; Week 2 of treatment), may be done by telephone; Week 4 (Visit 5; end of treatment/early termination); Week 6 (Visit 6; post-treatment follow-up), may be done by telephone. The end of the study is defined as the date of Visit 6. The schedule of evaluations for Study 3030-401-002 is presented in Table 4-1.

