5.0 OBJECTIVES

The primary objectives of this study are to evaluate the efficacy of eluxadoline 100 mg BID in IBS-D participants with evidence of BAM compared to IBS-D participants without evidence of BAM and to evaluate the safety and tolerability of eluxadoline 100 mg BID in IBS-D participants with evidence of BAM and in IBS-D participants without evidence of BAM. The secondary objectives of this study are to further evaluate the efficacy of eluxadoline 100 mg BID in IBS-D participants with evidence of BAM compared to IBS-D participants without evidence of BAM and to evaluate the population PK of eluxadoline in IBS-D participants with and without evidence of BAM.

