10.1 PRIMARY EFFICACY PARAMETER

The primary efficacy parameter will be the change from baseline in average BSFS score over 4 weeks of treatment period. The participant-reported BSFS is a 1 to 7 scale where 1 corresponds to a hard stool and 7 corresponds to watery stool. For each participant, all available (non-missing) postbaseline BSFS score of the treatment period will be used to calculate the average BSFS score.

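### The primary efficacy objective compares BAM with non-BAM, but the protocol and SAP text plan only separate cohort summaries, with no between-cohort difference or confidence interval

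*SAP*

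**What the plan says.** Protocol Section 4 sets the primary efficacy objective as a comparison of "IBS-D participants with evidence of BAM compared to IBS-D participants without evidence of BAM". SAP Section 5.0 repeats it: "to evaluate the efficacy of eluxadoline 100 mg BID in IBS-D participants with evidence of BAM compared to IBS-D participants without evidence of BAM". Protocol Section 5.4 justifies stool consistency as the primary outcome because it is "ideally suitable to detect potential differences in responsiveness to treatment among participants with and without evidence of BAM".

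The protocol carries two expectations for this contrast. Section 3.1 expects greater efficacy in participants without BAM. The clinical hypotheses in Section 4 expect similar effects on stool consistency in the two cohorts.

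The planned analysis is within-cohort only:

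- Protocol Section 10.3.1: "All efficacy endpoints will be summarized by participant cohort (BAM or Non-BAM) descriptively". Its Table 10-2 lists N1, mean, SD, median, minimum and maximum for continuous data.
- Protocol Section 10.3.2: "The following primary and secondary efficacy endpoints will be summarized by cohort (BAM or Non-BAM) for the mITT population". Tables 10-3 and 10-4 give a descriptive summary as the method for the primary endpoint and every secondary efficacy endpoint.
- SAP Section 10.0: "All efficacy endpoints will be summarized by participant group (BAM or Non-BAM"), with the same list of statistics.
- SAP Section 10.1: "The primary efficacy parameter will be the change from baseline in average BSFS score over 4 weeks of treatment period". It explains how the average is formed and adds no comparison. Sections 10.2 and 16.2 add none either.

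SAP Section 4.0 notes that "Specifications of tables, figures, and data listings are contained in a separate document".

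**The concern.** The question is about a difference between cohorts, and the plan produces two columns of summaries. The step from those columns to an answer is left to the reader, with no stated estimand, sign convention, method or measure of uncertainty.

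This matters more than usual because the protocol holds two opposing expectations. With small cohorts, two nearby means are easily read as showing a similar effect, and two moderately separated means as showing a greater effect without BAM. Neither reading is safe unless the uncertainty of the difference is in view. In an open-label study, an unstated method also leaves room to choose the form of the comparison after the data are seen.

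**Working it through.** **Inputs from the documents.** There are 12 participants per cohort (Protocol Section 10.1, SAP Section 14.0). The primary endpoint is each participant's change from baseline in average BSFS. The documents give no SD, effect size, alpha, power or margin, and they say the sample size has no statistical basis, so there is no planned figure to reproduce.

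**Assumptions.** All 24 participants are evaluable. The cohorts are treated as independent samples, because matching is only as far as possible, at the investigator's discretion (Protocol Sections 5.1 and 7.3), and no pairing rule is given. The SD of the change score is assumed and shown as a range.

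**Precision of the difference, equal SDs.**

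Half-width = t(0.975, 2n − 2) × SD × √(2/n)

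With n = 12: 2.0739 × 0.4082 × SD = 0.847 SD. Welch and pooled t agree here (22 df).

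| Assumed SD of change (BSFS points) | 95% CI half-width (points) |
|---|---|
| 0.6 | 0.51 |
| 1.0 | 0.85 |
| 1.5 | 1.27 |

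**Unequal SDs, assumed 0.6 and 1.5.** SE = √(0.36/12 + 2.25/12) = 0.466. Welch df = 14.4 and t = 2.139, so the half-width is 2.139 × 0.466 = 1.00 point.

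**Fewer evaluable participants.** Protocol Section 7.3 says those who discontinue may not be replaced. With 10 per cohort the half-width grows to 0.94 SD.

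**What this does to the two readings.**

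- Observed difference of zero: the interval is −0.85 to +0.85 SD, so it cannot support a claim of similar effects.
- Observed difference of 0.5 SD: 0.5 ± 0.847 gives −0.35 to 1.35 SD, so it cannot by itself support a claim of greater effect without BAM.

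**Why an estimate and not a test.** At two-sided 5%, power for a true 0.5 SD difference is about 22% (noncentral t). The difference detectable with 80% power is about 1.20 SD. A non-significant p-value would say almost nothing, whereas an interval shows directly what has and has not been ruled out.

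**The case against.** The strongest reply is that the plan is a disclosed and consistent choice. Protocol Section 5.4 says the study is not powered and aims at a qualitative view of whether response differs. Section 10.3.2 then applies descriptive methods throughout, and the SAP follows. Side-by-side summaries can be called a comparison on those terms. This stands as a defence against asking for a test or more participants, and neither is asked for. It does not show why the one quantity named in the objective should go unreported; an estimate with its interval is itself descriptive.

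Second, n, mean and SD of change in each cohort determine the unadjusted Welch difference and interval, so a reader could compute them. That is true, and it limits the harm. A baseline-adjusted estimate cannot be recovered that way, and the method would still not be prespecified.

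Third, the half-widths reflect the small sample, which the protocol accepts. They do not measure harm from omitting the interval, and printing it makes the study no more precise. That is correct: the gain lies in showing the uncertainty beside the conclusion.

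Fourth, the separate table specifications may contain a difference. That cannot be excluded. If they do, the SAP should say so.

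Fifth, matching is the plan's answer on comparability. Whatever it achieves, it gives neither the contrast nor its uncertainty.

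Finally, the two opposing hypotheses are a separate inconsistency. Reporting an interval does not reconcile them, and a conclusion of similarity would also need a margin, which the documents do not give.

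**Conclusion.** The concern holds for the protocol and SAP text. The primary efficacy objective is comparative, and no between-cohort estimate or interval is prespecified for it. With 12 evaluable per cohort, independent samples and equal SDs, the interval for the primary contrast would extend about 0.85 SD either side of the estimate. In points this depends wholly on the assumed SD, from 0.51 at an SD of 0.6 to 1.27 at an SD of 1.5. The study is not invalid as planned, and the lack of power is not a defect in a declared pilot. The change should be made because it is cheap and lets the study answer its own question with the uncertainty in view.

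**What to change.** Keep the descriptive tables and add to SAP Section 10.1:

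> The difference in mean change from baseline in average BSFS (BAM minus non-BAM; a positive value means less reduction in BSFS with BAM) will be presented with a two-sided 95% confidence interval (two-sample t, Welch). It is exploratory and no hypothesis test will be done. A supportive estimate from a linear model of change on cohort and baseline average BSFS will be shown beside it. In these non-randomized cohorts neither estimate removes all confounding.

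The Welch difference should be named as the main estimate, because the adjusted and unadjusted values can differ when baselines are not balanced by randomization.

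Optional in SAP Section 10.2: the same unadjusted difference and interval for the continuous secondary endpoints other than serum 7αC4, and a difference in proportions with a Newcombe interval for fecal incontinence, all labelled exploratory and not adjusted for multiplicity. As an illustration with assumed counts of 6/12 and 3/12, the incontinence difference is 25 percentage points (95% CI −12 to +54). Serum 7αC4 should stay descriptive. Cohorts can be selected on it (Protocol Section 6.1), and where the qualifying value is also the baseline value (SAP Section 10.0), regression to the mean would distort the contrast.

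The cost is a few lines of SAP text and a little programming, with no new data and no extra participants. The downside is a visibly wide interval that must be explained as exploratory. If the database is already locked, report the estimate and label it post hoc. If the sponsor does not want a contrast at all, the alternative is to reword the objective as a description of each cohort.

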Section 5.4 Scientific Rationale for Study Design	Updated with rationale for use of both serum 7αC4 testing and measurement of fecal bile acids to determine BAM status.	To update definition of BAM based on the most recent literature
Synopsis and Section 6.1 Inclusion Criteria	Amended IC 1.01: Participant is a man or woman aged 18 to 65–75 years, inclusive, at screening.	Approximately 25% of participants with chronic diarrhea or diarrhea predominant irritable bowel syndrome are found to have bile acid malabsorption. As there is not age restriction in developing bile acid malabsorption, Allergan believe it is critical to understand how this medication will affect this participant population.
Synopsis and Section 6.1 Inclusion Criteria	
Amended IC 2.03: Participants with evidence of BAM
 
Participants must have at least one of the following results from fasting serum 7αC4 level ≥ 52.5 ng/mL at screening or within 1 calendar year prior to screening.
 
 • fasting serum 7α-hydroxy-4-cholesten-3-one (7αC4) level ≥ 52.5 ng/mL • total fecal bile acids > 2337 micromoles/48 hours • primary bile acids (fecal CA and CDCA) $\geq 10\%$ in a 48h fecal collection • primary bile acids (fecal CA and CDCA) $\geq 4\%$ with total fecal bile acid $\geq 1,000$ micromoles/48hr 
Note: Participants may be enrolled as BAM positive without serum 7αC4 test results if they have positive results from 48 hour measurement of total fecal bile acids within 1 calendar year prior to
	To update definition of BAM based on the most recent literature

Eluxadoline

Section No. and Name	Description of Change	Rationale
Synopsis and Section 6.1 Inclusion Criteria	
screening, defined by total fecal BA > 2337 micromoles/48 hours.
 
Amended IC 2.04: Participants without BAM
	

Participants must have **at least one of the following results from fasting serum 7αC4 level ≤ 47.1 ng/mL** at screening or within 1 calendar year prior to screening.

- **fasting serum 7αC4 level ≤ 47.1 ng/mL**
- **fasting serum 7αC4 levels > 47.1 ng/mL but < 52.5 ng/mL with fecal bile acids that are negative for bile acid malabsorption (i.e. do not meet criteria 2.03 based on fecal bile acids level)**
- **total fecal bile acids (BA) ≤ 2337 micromoles/48 hours**
- **primary bile acids (fecal CA and CDCA) $< 10\%$ in a 48h fecal collection**
- **primary bile acids (fecal CA and CDCA) $< 4\%$ with total fecal bile acid $< 1,000$ micromoles/48hr**

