The typical proportion of primary fecal bile acids in healthy volunteers is $\sim 0.2\%$. Patients with BAM have higher stool weight compared to those with chronic diarrhea without BAM or healthy volunteers ([Vijayvargiya 2018](#)). The sensitivity and specificity of the fecal biomarkers of BAM are listed in [Table 5-2](#). Therefore, elevated primary BA alone or in combination with total fecal bile acids of $\geq 1000 \mu\text{mol}/48 \text{ hr}$ have a similar diagnostic accuracy as total fecal BA alone of $> 2337 \mu\text{mol}/48 \text{ hr}$ in detecting elevated fecal weight in patients with BAM. Statistical analysis has demonstrated no significant difference between the ROC curve to estimate elevated fecal weight for either total BA or elevated primary fecal BA ($p=0.13$). After increasing the primary

Eluxadoline

BA cutoff to 10% or higher with total fecal BA $\geq 1000 \mu\text{mol}/48 \text{ hr}$, there was no significant gain in either sensitivity (41%) or specificity (97%) compared to the lower cutoff of primary BA $\geq 4\%$ with total fecal BA $\geq 1,000 \mu\text{mol}/48 \text{ hr}$ ([Vijayvargiya 2018](#)).

Therefore, even at the lower cutoff values of $\geq 4\%$, primary fecal bile acids are indicative of BAD even though the total fecal BA may be only $1000 \mu\text{mol}/48 \text{ hr}$.

However, in an analysis of 986 patients who underwent 48 hour fecal BA evaluation for chronic diarrhea, 26% of patients had elevated total fecal bile acids whereas 46% of patients had fecal primary bile acids $\geq 10\%$, indicating that measuring total fecal bile acids alone will miss a subgroup of patients who have features of BAM ([Vijayvargiya 2018](#)).

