10.1. Sample Size Determination

The total sample size for this study is 24 participants (12 participants with BAM and 12 participants without BAM). No formal sample size estimation will be calculated because the sample size for this study is not based on statistical consideration.

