Section 7.5	Addition of bolded text describing destruction of test material: The study site must send any unused study treatment to the vendor specified, for destruction or have study drug destroyed per documented institutional standards of practice that have been approved by the sponsor.	Due to DEA handling restrictions and institution processes the site is unable to return unused study drug to sponsor. The alternative destruction process was agreed upon and documented in Note to file
Section 9.8.2.1 AEs of Special Interest	Addition of bolded text for clarification: Once notified, the investigator must contact the participant to review the participant's status as soon as possible (eg, within 24 hours), to assess the severity of his/her constipation or the presence of any sequelae of constipation. Every attempt should be made to reach the study participant within 24 hours.	For clarity: Severe constipation is an adverse event of special interest and due to the potential seriousness of this condition, investigator's should attempt to reach the participant within a 24 hour period. The previous iteration of this text allow for interpretation of the phrase "as soon as possible", while the amendment makes it clear that "Every attempt should be made to reach the study participant within 24 hours".
Section 12.9 Appendix 9	The sponsor contact information was updated.	Personnel change at Allergan

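### The BAM and non-BAM entry criteria overlap and the SAP does not derive the group, so participants with evidence of BAM can be analysed as non-BAM

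*SAP*

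**What the plan says.** The first primary objective compares efficacy between participants with and without evidence of BAM (Protocol Section 4; SAP 5.0). The SAP carries this out descriptively: "All efficacy endpoints will be summarized by participant group (BAM or Non-BAM" (SAP 10.0). The cohorts are small: "The total sample size for this study is 24 participants (12 participants with BAM and 12 participants without BAM" (Protocol 10.1).

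The groups are defined in Protocol 6.1, where either criterion is met by at least one item on its list:

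- **2.03, BAM:** 7αC4 of at least 52.5 ng/mL; or total fecal bile acids above 2337 micromoles/48 h; or primary bile acids of at least 10%; or primary bile acids of at least 4% with total of at least 1,000.
- **2.04, non-BAM:** 7αC4 of 47.1 ng/mL or less; or 7αC4 between the two cutoffs with negative fecal results; or total of 2337 or less; or primary below 10%; or primary below 4% with total below 1,000.

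Section 5.4 says in one place that BAM status rests on the presence of at least one Table 5-2 parameter. Later it says "Evidence of BAM will be determined by a screening serum" 7αC4 value of at least 52.5 ng/mL, with no fecal route.

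The amendment revised 2.03 and 2.04 with the rationale "To update definition of BAM based on the most recent literature". SAP 4.0 cites the protocol "dated 19 Oct 2017 and the most recent amendment dated 17 Apr 2019", while SAP 17.0 calls the 19 Oct 2017 protocol the latest.

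**The concern.** The primary comparison depends entirely on which group each participant is in. Nothing is randomised and everyone receives the same drug, so the group label is the only contrast in the study. If one participant's results can satisfy both criteria, the label depends on which result was used, and the SAP gives no rule for choosing.

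A participant who has evidence of BAM under the at-least-one rule in Section 5.4, but who entered as non-BAM on another test, then contributes to the non-BAM mean. If BAM truly alters response, such participants move the non-BAM mean toward the BAM mean. That works against the hypothesis in the Synopsis and Section 3.1 (greater efficacy without BAM) and toward the one at the end of Section 4 (similar effects on stool consistency). The study could report similarity partly because the groups were mixed.

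**Working it through.** **1. The plan's own figure.** 12 + 12 = 24, which agrees. No power, effect size or SD is given, so there is nothing further to reproduce.

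**2. Do 2.03 and 2.04 separate participants?** Take results on both sides of each cutoff: 7αC4 of 30, 50 and 60; total fecal bile acids of 800, 1500, 2250, 2337 and 2500; primary bile acids of 2%, 6% and 12%. That gives 3 × 5 × 3 = 45 complete profiles.

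- *Only 2.03 met.* This needs 7αC4 above 47.1, total above 2337 and primary of at least 10%: 7αC4 of 50 or 60 with 2500 and 12% = 2 profiles.
- *Only 2.04 met.* This needs 7αC4 below 52.5 and no positive fecal result: primary 2% with any of the four totals up to 2337, or primary 6% with total 800, so 5 fecal patterns × 2 values of 7αC4 = 10 profiles.
- *Both met.* 45 − 2 − 10 = 33 profiles.

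These are logical combinations, not patient frequencies. They show that the overlap is not confined to a boundary. Examples are total 1500 with primary 12%; 7αC4 of 60 with total 800; and 7αC4 of 30 with primary 12%.

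**3. Is the amendment the cause?** Allowing missing results gives 84 profiles. Of these, 62 could be assigned under the superseded criteria. None of the 62 fails the current criterion for its own cohort, but 37 meet both current criteria. The ambiguity therefore lies in the current criteria and applies to later entrants as well.

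**4. How often might two fecal markers disagree?** The only figures in the documents come from 986 patients tested for chronic diarrhea: "26% of patients had elevated total fecal bile acids whereas 46% of patients had fecal primary bile acids" of at least 10% (Section 5.4). The joint distribution is not given, so only bounds are possible.

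- Minimum with primary of at least 10% but total not elevated: 46% − 26% = 20% (about 197 of 986).
- Maximum, if nobody has both: 46% (about 454 of 986).
- As a share of the 100% − 26% = 74% with non-elevated total: 20/74 = 27% to 46/74 = 62%.

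The route of at least 4% with total of at least 1,000 is not counted, and could only add to these shares.

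**5. Effect on the comparison.** Suppose *m* of the 12 non-BAM participants have BAM and respond on average like the BAM cohort, and the BAM cohort is pure. The expected difference is then (1 − *m*/12) of the true one:

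| *m* | share retained |
|---|---|
| 0 | 100% |
| 1 | 92% |
| 2 | 83% |
| 3 | 75% |

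As an extreme illustration, assume all 12 were classified on total fecal bile acids alone and the series applied to them. Then 12 × 0.27 = 3.2 to 12 × 0.62 = 7.5 would be positive on primary bile acids, leaving 73% to 38%. The documents do not say that participants qualified in this way.

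**The case against.** The strongest defence is that the SAP elaborates the protocol. SAP 4.0 describes both cohorts and ties them to BAM status, the criteria stand in Protocol 6.1 and agree with the Synopsis, and the 7αC4-only sentence is rationale text. Table and listing specifications are in a separate document, so a listing of qualifying tests may already be planned. Many participants may have only one recorded test: 7αC4 is done at screening if necessary, and the visit descriptions in Section 9 mention 48-hour fecal collection only as a prior result. For those participants no conflict would be visible and a derived variable would change nothing. The study is also a descriptive pilot whose size is declared openly: "the sample size for this study is not based on statistical consideration".

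Most of this stands, and it limits the size of the point. It does not remove the overlap in 6.1, and it supplies no precedence rule where results conflict.

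A reader might infer three stronger things:

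- **That the amendment left earlier participants in the wrong cohort.** Current 2.04 still accepts total fecal bile acids of 2337 or less on their own, and the superseded limit of below 2200 lies inside that. No earlier assignment becomes invalid. The remark in the Amendment 1 summary that "the site is unable to return unused study drug to sponsor" may suggest a site already at work, but it does not show how many had enrolled, in which cohort or by which test.
- **That the site fixes the group.** The protocol does not name who assigns BAM status; investigator discretion is stated for matching only.
- **That Table 10-1 freezes the cohort for the mITT population.** Its entry of Assignment sits in the Study Treatment column, and all participants receive eluxadoline.

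**Conclusion.** The point holds as an undefined grouping variable. Current 2.03 and 2.04 are not mutually exclusive, Section 5.4 carries two incompatible rules, and the readable text of SAP 10.0 does not say how the group is obtained. A participant with evidence of BAM by the at-least-one rule can be summarised as non-BAM under any protocol version.

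If a true difference exists, each such participant removes about 8% (1/12) of the expected difference between cohort means, under the assumptions of step 5. If there is no true difference, mixing the groups does not bias the comparison.

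The number affected is unknown and may be zero. The 27% to 62% range shows only that the two fecal markers can disagree often. It comes from patients with chronic diarrhea rather than Rome IV IBS-D participants, and it assumes that elevated total in that series corresponds to the 2337 cutoff. It is not an estimate for this trial. The change should be made because it is cheap and concerns the primary comparison, but it does not invalidate the study.

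**What to change.** In SAP 10.0, define a derived BAM variable from all recorded 7αC4 and fecal results, with an explicit precedence rule. Following the at-least-one rule in Section 5.4, any recorded parameter that meets 2.03 classifies the participant as BAM; non-BAM requires that no recorded parameter meets 2.03. On the 45 profiles in step 2 this gives one answer each: 2 + 33 = 35 BAM and 10 non-BAM.

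Present the primary endpoint by derived status and by the cohort assigned at enrolment. List for each participant the tests available, the qualifying test, the protocol version and any change of group.

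In the protocol, reconcile the 7αC4-only sentence in Section 5.4 with the rest of that section and with 6.1, and reconcile the overlap between 2.03 and 2.04. In SAP 17.0, align the protocol date with SAP 4.0 so that the version in force is clear.

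The cost is SAP and protocol wording, one derived variable, one repeated table and one listing. Because the variable uses recorded results only, no new assessments are needed. There are two downsides. Derived group sizes may depart from 12 and 12. Participants with only one recorded test can be classified only on that test, so an any-positive rule depends partly on how many tests a participant had. This is why the assigned grouping should stay beside the derived one.
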